9.4. PK analysis

Plasma concentrations for JNJ-67953964 will be analyzed. Based on the individual plasma concentration-time data from all subjects, exposure parameters of JNJ-67953964 will be derived using population PK (popPK) modeling. Potential baseline covariates (eg, demographics such as age, sex and race, body weight, laboratory variables such as creatinine clearance, etc.) may be included in the models, if relevant. The following exposure parameters will be derived using Bayesian feedback analysis: AUC_{24h} and C_{0h}. Results will be tabulated and summary statistics will be generated. Individual plasma concentrations per study visit will be listed. PK and PD relationship will be explored, if feasible. Details of population PK analysis and PK/PD analysis will be given in an analysis plan and the results will be presented in a separate report.

9.5. Safety Analyses

Statistical analysis of the safety data will be done by the sponsor or under the authority of the sponsor. Specific details will be provided in the Statistical Analysis Plan.

All safety analyses will be performed based on the safety analysis set, which will include all randomized subjects who receive at least 1 dose of study drug. Safety summaries will be provided by treatment, unless specified otherwise.

AEs will be coded using the current version of Medical Dictionary for Regulatory Activities (MedDRA) and tabulated by system organ class, by severity and relationship to study drug and will be presented by treatment. SAEs will be summarized separately.

The safety analysis will include the incidence of AEs, actual data and changes in blood pressure, pulse rate, laboratory safety data, 12-lead ECG and physical and neurological examination data from predose to all postdose assessments.

The suicidal ideation and suicidal behavior data collected from the C-SSRS will be summarized descriptively at each scheduled timepoint by treatment group. Sexual dysfunction (ASEX) and KSS data collected will be summarized descriptively at each scheduled timepoint by treatment group.

Adverse Events

The verbatim terms used in the CRF by investigators to identify AEs will be coded using the MedDRA. All reported AEs with onset during the double-blind treatment phase (i.e., TEAEs, and AEs that have worsened since baseline) will be included in the analysis. For each AE, the percentage of subjects who experience at least one occurrence of the given event will be summarized by treatment group. Summaries will be provided for all subjects receiving at least one dose of study drug in this study, and will include AEs from this study.

Summaries, listings, datasets, or subject narratives may be provided, as appropriate, for those subjects who die, who withdraw due to an AE, or who experience a severe AE or a SAE.

Clinical Laboratory Tests

Laboratory data will be summarized by type of laboratory test. Descriptive statistics will be calculated for each laboratory analyte at baseline and at each scheduled time point, and for changes from baseline.

The number and percentage of subjects experiencing a laboratory result below or above normal reference ranges will be provided for each laboratory analyte by treatment group. Summaries will be provided for all subjects receiving at least one dose of study drug in this study.

A listing of subjects with any laboratory result outside the reference ranges will be provided.

ECG

Heart rate and ECG intervals (RR, PR, QRS and QT) as well as corrected QT intervals according to Bazett's formula (QTcB) and Fridericia's formula (QTcF) (Bazett 1920, Sagie 1992, Hodges 1983, International Conference on Harmonization [ICH] 2005) from the 12-lead ECG will be summarized at baseline and at each scheduled time point and for changes from baseline using descriptive statistics.

The number and percentage of subjects with at least one occurrence of a treatment-emergent potentially clinically important QTc measurement (QTc value >450 , >480 , or >500 msec) or with a change from baseline in QTc >30 msec or 60 msec, will be summarized by treatment group.

Data listings of subjects with any potentially clinically important values or with a change from baseline in QTc will be provided.

Vital Signs

Descriptive statistics of temperature, pulse, and blood pressure (systolic and diastolic) values and changes from baseline will be summarized at each scheduled time point. The percentage of subjects with values beyond clinically important limits will be summarized.

Physical and Neurological Examinations

Subjects with abnormal findings will be presented in a data listing.

Other Safety Measures

C-SSRS

The suicidal ideation and behavior data collected from the C-SSRS will be summarized descriptively at each scheduled timepoint by treatment group. Data from the subjects with suicidal ideation and behavior will be presented in data listing.

ASEX and KSS

Sexual dysfunction and KSS data collected will be summarized descriptively at each scheduled timepoint by treatment group.

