The treatment phase of the trial will consist of 3 periods. A placebo lead-in period of concealed duration, after which subjects will enter the double-blind treatment period when they will be randomly assigned to 10 mg JNJ-67953964 or continue placebo for 6 weeks. Subjects who complete the treatment period, will then enter the withdrawal period and be treated with placebo for the remaining time of the treatment phase of the study. The total study duration for each subject will be approximately 16 weeks. There will be 11 scheduled visits to the clinical research center including screening during the study. An overall flow diagram of the study is shown in Figure 1.

Figure 1: Flow diagram of the study

Eligibility Screening Examination

After giving written informed consent, subjects will be screened within 35 to 2 days prior to Day 1 to ascertain their eligibility for the study per the inclusion and exclusion criteria. Upon completion of all informed consent form (ICF) procedures, recording of adverse events (AEs) and concomitant medication will start. Each subject in this study must have their current study participation status checked by a clinical trials verification system when such a system is available for this study.

The symptoms of depression will be assessed using the (structured interview guide for the) MADRS.

Double-blind Treatment Phase

The duration of the double-blind treatment phase will be 11 weeks divided into 3 periods. Subjects will visit the study center for baseline visits on Day 1. The subject will receive study medication after completion of the visit on Day 1. The first dose will be taken at home on Day 2.

Medication will be dispensed at each study visit during this double-blind period. All study medication will be taken in fasting condition.

During the double-blind study phase, the subjects will visit the study center for out-patient visits every 1 to 2 weeks as indicated in the [Time and Events Schedule \(TES\)](#).

Lead-in period

Subjects who successfully complete the baseline examination visit at the clinical site/unit, will be treated with placebo for the entire duration of the lead-in period. Investigators and subjects will be blinded to the exact duration of lead-in period for each subject in the study.

Treatment period

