Biomarker levels will be tabulated for each time point and summary statistics will be calculated. Posttreatment changes in biomarker levels will be assessed by treatment group. Analysis of variance (ANOVA) and t-test will be used to assess differences across groups and time points. Correlations between biomarker levels and clinical endpoints will be evaluated.

All biomarker data obtained from this study may also be included in an ongoing cross-study analysis to investigate the relationship between depression severity, phenotypes, and biomarkers.

Pharmacokinetic Analyses

Plasma concentrations for JNJ-67953964 will be analyzed. Based on the individual plasma concentration-time data from all subjects, exposure parameters of JNJ-67953964 will be derived using population PK (popPK) modeling. Potential baseline covariates (eg, demographics such as age, sex and race, body weight, laboratory variables such as creatinine clearance, etc.) may be included in the models, if relevant. The following exposure parameters will be derived using Bayesian feedback analysis: AUC_{24h} and C_{0h}. Results will be tabulated and summary statistics will be generated. Individual plasma concentrations per study visit will be listed. Pharmacokinetic and pharmacodynamic relationship will be explored, if feasible. Details of population PK analysis and PK/PD analysis will be given in an analysis plan and the results will be presented in a separate report.

Safety analyses

Statistical analysis of the safety data will be done by the sponsor or under the authority of the sponsor. Specific details will be provided in the Statistical Analysis Plan.

All subjects receiving at least one dose of study drug will be included in the safety analysis.

AEs will be coded using the current version of Medical Dictionary for Regulatory Activities (MedDRA). All reported AEs with onset during the double-blind treatment phase (i.e., treatment-emergent adverse events [TEAEs], and AEs that have worsened since baseline) will be included in the analysis. Serious adverse events (SAEs) will be summarized separately.

Laboratory data will be summarized by type of laboratory test and treatment. Descriptive statistics will be calculated for each laboratory analyte at baseline and at each scheduled time point, and for changes from baseline. The percentage of subjects with values out of normal limits will be summarized. Data listings of subjects with at least one abnormal value will be provided.

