1.2. Time and Events Schedule (TES)^a

Phase	Screening	Double-blind treatment phase ^a									
Visit number	1	2	3	4	5	6	7	8	9	10	11 or EW ^b
Week (end of)	-5 to 0	0	1	2	3	4	6	7	8	9	11
Study Day	-35 to -2	1	8	15	22	29	43	50	57	64	78
Screening											
Informed consent	X										
Medical History and study participation status	X										
Demographic information	X										
Prestudy therapy by ATRQ	X										
Serology, thyroid function, HbA1c (only in diabetic subjects)	X										
MINI 7.0 interview	X										
Download and install app(s) at screening and baseline ^m	X	X									
Inclusion/exclusion criteria	X	X									
Safety assessments											
Physical and neurological examination	X	X				X					X
Height	X										
Weight	X	X									X
Urine drug and alcohol breath test	X	X									
Pregnancy test ^c	X	X				X					X
12-Lead ECG	X	X			X	X	X			X	X
Vital signs (supine BP, pulse)	X	X	X	X	X	X	X	X	X	X	X
Tympanic or oral temperature	X	X			X	X	X			X	X
ASEX		X			X	X	X			X	X
KSS		X			X	X	X			X	X
Suicidality by C-SSRS	X	X	X	X	X	X	X	X	X	X	X
Dosing											
Randomization		X	X	X	X						
Supply new study medication		X	X	X	X	X	X	X	X	X	X
Oral dose study medication ^d						Day 2 until and including Day 78 ^e					
Meal after dosing		X ^f	X ^f	X ^f	X ^f	X ^f	X ^f	X ^f	X ^f	X ^f	X ^f
Blood and urine collection											
Clinical laboratory Tests: hematology, serum chemistry, and urinalysis	X ^f	X ^f				X ^g			X ^g		X ^g
Gastric mucosa panel		X ^f				X ^g					X ^g
Supply subject with tubes for saliva collection	X				X				X		
Saliva collection for cortisol		X ^h				X ^h					X ^h
Blood sample for pharmacokinetics	X			X ⁱ	X ⁱ	X ⁱ					X ⁱ
Blood sample for biomarkers and (epi)genetics		X ^f			X ^g				X ^g		
Clinical Assessments											
Structured Interview Guide MADRS	X ^j	X	X	X	X	X	X	X	X	X	X
Structured Interview Guide SIGH-A		X	X	X	X	X	X	X	X	X	X
CGI-S		X	X	X	X	X	X	X	X	X	X
SMDDS		X			X	X	X				X
CPFQ		X			X	X	X				X
SHAPS	X	X	X	X	X	X	X	X	X	X	X
SATE ^k						once weekly while at home					
Ongoing subject review											
Assessment of subject study engagement ^k	X					up to 3 occasion when at home					
Adverse events						continuous					
Concomitant medication						continuous					

^a This section has been amended by amendment INT-1 and INT-2

EW= early withdrawal

- (a) Visits should be conducted \pm 3 days of the scheduled day (based on Visit 2, not based on previous visit).

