The treatment phase of the trial will consist of 3 periods. A placebo lead-in period of concealed duration, after which subjects will enter the double-blind treatment period when they will be randomly assigned to 10 mg JNJ-67953964 or continue placebo for 6 weeks. Subjects who complete the treatment period, will then enter the withdrawal period and be treated with placebo for the remaining time of the treatment phase of the study. The total study duration for each subject will be approximately 16 weeks. There will be 11 scheduled visits to the clinical research center including screening during the study. An overall flow diagram of the study is shown in Figure 2:

Figure 2: Flow diagram of the study

Eligibility Screening Examination

After giving written informed consent, subjects will be screened within 35 to 2 days prior to Day 1 to ascertain their eligibility for the study per the inclusion and exclusion criteria. Upon completion of all informed consent form (ICF) procedures, recording of AEs and concomitant medication will start.

The symptoms of depression will be assessed using the (structured interview guide for the) MADRS.

Double-blind Treatment Phase

The duration of the double-blind treatment phase will be 11 weeks divided into 3 periods. Subjects will visit the study center for baseline visits on Day 1. The subject will receive study medication after completion of the visit on Day 1. The first dose will be taken at home on Day 2.

Medication will be dispensed at each study visit during this double-blind period. All study medication will be taken in fasting condition.

During the double-blind study phase, the subjects will visit the study center for out-patient visits every 1-2 weeks as indicated in the TES.

Lead-in period

Subjects who successfully complete the baseline examination visit at the clinical site/unit, will be treated with placebo for the entire duration of the lead-in period. Investigators and subjects will be blinded to the exact duration of lead-in period for each subject in the study.

Treatment period

At the end of the lead-in period both placebo lead-in responders and placebo lead-in non-responders will be randomized to receive either placebo or 10 mg JNJ-67953964 in a 1:1 ratio for 6 weeks. Investigators and subjects will remain blinded to exact timing of the randomization, response criterion and study drug treatment assignment for each subject.

Withdrawal period

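### The adverse-event window in Protocol section 9.5 spans all 11 weeks, including the all-placebo lead-in and withdrawal; on the natural reading this pulls the relative drug-placebo contrast towards 1 (minor)

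*Protocol*

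**What the plan says.** Section 9.5 counts "All reported AEs with onset during the double-blind treatment phase (i.e., TEAEs, and AEs that have worsened since baseline"; the synopsis uses the same window, "All reported AEs with onset during the double-blind treatment phase". The measure is subject incidence: "the percentage of subjects who experience at least one occurrence of the given event will be summarized by treatment group". The same section also states "Safety summaries will be provided by treatment, unless specified otherwise", without saying whether that means the randomised group or the treatment being taken at onset. The safety set is randomised subjects with at least one dose, and specific details are left to a Statistical Analysis Plan.

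The window is the whole post-baseline study. Section 4.1 says "The duration of the double-blind treatment phase will be 11 weeks divided into 3 periods" and the synopsis says "The treatment phase of the trial will consist of 3 periods". The Time and Events Schedule puts one phase heading over Visits 2 to 11, with dosing from "Day 2 until and including Day 78". In the first period every subject "will be treated with placebo for the entire duration of the lead-in period"; 6 weeks of 1:1 randomised treatment follow, then placebo for everyone to the end.

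The supplied SAP is the population PK and PK/PD plan. Its section 3.1 uses treatment baseline for safety parameters and leaves lead-in data out. Its section 4.8 counts pruritus and GI subclasses from Day 22 to Day 64. Both rules serve its exposure-safety exploration only.

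**The concern.** Active drug can be taken in only 6 of the 11 weeks in which events are counted. A lead-in event arises on placebo whichever arm the subject later joins, so on the randomised-group reading it adds the same expected amount to both columns. This does not favour one arm. It moves the ratio of the two percentages towards 1, so the drug looks closer to placebo than it was while being taken.

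The clause on worsening since baseline does not cure this. The only baseline visit the protocol names is Visit 2 (section 8.2.2), before the lead-in, and section 9.5 does not use the *treatment baseline* that section 9.2.1 uses for efficacy.

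Safety and tolerability is a secondary objective, with pruritus and GI complaints as events of special interest. As written, the section 9.5 tables and the exposure-safety plots could report different counts of the same events.

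**Working it through.** **Period lengths.** SAP Table 1 puts treatment Day 1 at Day 22 and treatment Week 6 at Day 64; the last visit is Day 78.
- Lead-in: (22 − 1)/7 = 3 weeks
- Treatment: (64 − 22)/7 = 6 weeks
- Withdrawal: (78 − 64)/7 = 2 weeks

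The sum is 11 weeks, which reproduces the protocol's figure. Active exposure is possible in 6/11 = 55% of the window. The plan states no adverse-event rate or risk ratio, so there is nothing further of its own to reproduce.

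**Uncommon events.** Assume constant weekly risk and independent onsets in each period. With true on-treatment risk ratio RR and k = lead-in weekly risk divided by later placebo weekly risk:

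observed RR (lead-in + treatment) = (6·RR + 3k)/(6 + 3k)

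For all 11 weeks with k = 1 and equal withdrawal-period risk in both arms, it is (6·RR + 5)/11.

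| True RR | Lead-in included, k = 1 | k = 0.5 | k = 2 | All 11 weeks, k = 1 |
|---|---|---|---|---|
| 3.0 | 2.33 | 2.60 | 2.00 | 2.09 |
| 2.0 | 1.67 | 1.80 | 1.50 | 1.55 |
| 1.5 | 1.33 | 1.40 | 1.25 | 1.27 |

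**Finite risks (assumed).** Let h0 and h1 be weekly risks on placebo and drug. Treatment weeks only: a6 = 1 − (1 − h1)^6 and p6 = 1 − (1 − h0)^6. With the lead-in: a9 = 1 − (1 − h1)^6(1 − h0)^3 and p9 = 1 − (1 − h0)^9.

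| h0 / h1 | Treatment weeks, drug vs placebo | RR | Lead-in added, drug vs placebo | RR | Fall in difference |
|---|---|---|---|---|---|
| 0.5% / 1.5% | 8.7% vs 3.0% | 2.93 | 10.0% vs 4.4% | 2.27 | 0.1 points |
| 1% / 3% | 16.7% vs 5.9% | 2.85 | 19.2% vs 8.6% | 2.22 | 0.3 points |
| 2% / 4% | 21.7% vs 11.4% | 1.90 | 26.3% vs 16.6% | 1.58 | 0.6 points |
| 3% / 5% | 26.5% vs 16.7% | 1.59 | 32.9% vs 24.0% | 1.37 | 0.9 points |

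The difference shrinks only by the factor (1 − q), where q is the lead-in risk. It therefore moves little unless events are very common: an assumed 40% vs 20% over 6 weeks gives q = 1 − 0.8^0.5 = 10.6%, and 20.0 points becomes 17.9.

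**Earlier-study reading.** Protocol section 2.2.2 describes Study G by events above 5% and at least double placebo. Take 142 × 0.90 ≈ 128 randomised, or 64 per arm, since lead-in responders are randomised too. The exact binomial chance of meeting both conditions, under assumed 6-week risks, is:

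| Drug vs placebo | Treatment weeks only | Lead-in added |
|---|---|---|
| 5% vs 2.5% | 0.327 | 0.373 |
| 6% vs 3% | 0.413 | 0.415 |
| 8% vs 4% | 0.512 | 0.434 |
| 10% vs 5% | 0.546 | 0.421 |
| 20% vs 10% | 0.545 | 0.344 |

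**The case against.** The strongest reply is that section 9.5 defers specific details to a Statistical Analysis Plan, the clinical SAP is not in the file, and a treatment-emergent window is what such a plan normally sets. The one safety window that can be seen, in the PK/PD SAP, already separates the periods. This stands as a limit: a reader might infer that the trial's tables were in fact diluted, and the documents do not show that. It does not remove the point, because section 9.5 states a rule, the rule includes the lead-in, and no supplied document overrides it for the between-group tables.

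The columns are also not fixed. Tabulating by treatment could mean treatment at onset, which would put lead-in events under placebo. Section 4.2 once calls the 6 weeks the phase, although the 11-week use dominates. So the dilution is conditional on the more natural reading, and equal entry into both arms holds in expectation, not in each sample.

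The effect is on a ratio that the protocol does not plan to report. Section 9.5 gives percentages and plans no adverse-event test, and the difference in percentages barely moves. Tables by severity and relationship, and narratives for moderate or severe events of special interest, remain available. This stands and is why the point is minor.

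A reader might also infer that uncommon drug-related events would escape notice under the Study G description. The calculation does not support this: for 6% vs 3% the chance of meeting both conditions does not fall, and for 5% vs 2.5% it rises, because the lead-in helps lift the drug arm above 5%. The loss appears only for commoner events. That description also belongs to a completed study and is not a rule of this trial.

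**Conclusion.** The point holds as a minor fault in the protocol text. Followed as written, with columns by randomised group, section 9.5 attenuates the relative adverse-event contrast: a true risk ratio of 2.0 appears as about 1.67 with the lead-in included (1.50 to 1.80 as the lead-in weekly risk runs from double to half the later placebo risk), and as about 1.5 over all 11 weeks.

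These sizes rest on assumed rates and on independence between lead-in and later onsets; if the same subjects tend to have events in both periods, the dilution is smaller. The 11-week figure also assumes equal withdrawal-period risk. That need not hold, because section 4.2 expects the period to show any withdrawal symptoms after the drug, so those weeks could distort the contrast in either direction. The difference in percentages falls by under 1 point in the four weekly-risk scenarios with the lead-in included. No planned test or decision rule is affected.

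**What to change.** In section 9.5, for the between-group tables:
- Define a treatment-emergent event as onset or worsening relative to treatment baseline, from the first dose of the treatment period to the end of that period, with columns by randomised group.
- Tabulate lead-in events separately (all on placebo) and withdrawal-period events separately by randomised arm.
- Assign each event to one period by its onset date. If a residual-exposure window is wanted, show it as a supplementary table so that it does not overlap the withdrawal table.

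This matches the baseline and window in PK/PD SAP sections 3.1 and 4.8. Reconcile *phase* and *period* across Protocol sections 2.3, 4.1, 4.2 and 8.2.3. If the clinical SAP already does all this, a citation in section 9.5 is enough.

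The cost is some wording, period flags derived from onset dates and a few more tables. One constraint applies: the lead-in length is concealed from sites, so the protocol should use only the terms treatment baseline and treatment period, with calendar days kept in a SAP that sites do not hold.
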